8.7 Derived and Computed Variables

Demographics

Age will be calculated in years using the following formula:

$$(\text{Date of Visit 1} - \text{Date of Birth} + 1) / 365.25$$

Body Mass Index (kg/m²) will be calculated using the following formula:

$$\text{Weight (kg)} / \text{Height}^2 (\text{m}^2)$$

Immunogenicity

Values below the limit of quantification (LLQ = 1:100, recorded as “< LLQ”) will be set to half that limit (i.e., LLQ/2 = 1:50).

Geometric Mean Titer

The GMT will be calculated using the following formula:

$$10^{\left\{ \frac{\sum_{i=1}^n \log_{10}(t_i)}{n} \right\}}$$

where t_1, t_2, \dots, t_n are n observed immunogenicity titers/concentrations.

Ratio greater or equal to a given threshold is defined for non-missing values as:

= 1, if the concentration relative to pre-vaccination is superior or equal to the given fold-rise threshold

= 0, otherwise

Value of 4 fold-rise will be used.

Duration in the Study

Duration in the study is defined in days as:

Last visit date (visit x)^a – Enrollment date (visit 1) + 1

^aor premature discontinuation date (in case of withdrawal from the study)

The duration is missing if one of the dates is missing or incomplete.

Duration in the study after vaccination 1 is defined in days as:

Date of vaccination 2 (visit 5) – Date of vaccination 1 (visit 2)

Duration in the study after vaccination 2 is defined in days as:

Date of vaccination 2 follow-up (visit 9) – Date of vaccination 2 (visit 5)

Solicited Adverse Events

For details see [section 13.2](#).

Unsolicited Adverse Events

All adverse events will be characterized according to the date of occurrence related to the vaccination phase as follows:

- **Emergence before vaccination phase:** start date before the first date of injection of study vaccine.
- **Emergence during vaccination phase:** start date on or after the first date of injection of study vaccine or, adverse event increase in severity including to “serious” adverse event.

If start date is equal to the first date of injection then “timing” variable (“On injection day, before injection”/“On injection day, after injection”) will be used to define whether the adverse event occur before or after the injection.

If there are several vaccinations, the adverse event will be associated with the most recent vaccination.

If an adverse event start date is missing or unknown, the adverse event will be considered as emergent.

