When start and/or end dates of an adverse event are only partially known, adverse events will be categorized as emergent before, during, or after vaccination phase using the following rules:

- If the partial end date is before ($<$) the first study vaccination (i.e., year or year & month is/are before the first study vaccination year or year & month) then the adverse event is emergent before vaccination phase.
- If the partial start date is equal or after (\geq) the first study vaccination (i.e., year or year & month is/are after or the same as the first study injection year or year & month) then the adverse event is emergent during vaccination phase.

The **maximum event severity** is the greatest severity associated with a preferred term (PT) for a reported adverse event according to the following order: Mild $<$ Moderate $<$ Severe. Unknown/ Missing severity is considered as severe (except for the definition of emergence).

Multiple AEs with the same PT for the same subject are counted only once.

Vaccination-related Adverse Events are those for which the relationship has been evaluated by the investigator, and recorded either as possibly related, probably related or unknown/ missing.

Safety Laboratory Data

All laboratory measurements summarized in the CSR are those defined in the study protocol. All laboratory tests including retests and reasons for retests will be presented in the data listings for each subject. In case of multiple measurements of a laboratory parameter for a subject:

1. Before the study vaccination, only the latest measurement, with closest date before ($<$) the first study vaccination date, will be retained for analysis.
2. After the study vaccination, only the first measurement, with soonest date after ($>$) the last study vaccination date, will be retained for analysis.

Reference ranges used to categorize the results as “low” (values below the lower limit of the reference range), “normal” (values within the reference range) or “high” (values above the upper value of the reference range) will be those provided by Quintiles Laboratories, which performed the tests and provided the laboratory reports.

Pre-study, Concomitant and Post-Vaccination Medications

A **previous medication** is a medication used only before the first study vaccination (i.e. medication end date < first study vaccination date).

All other medications are **concomitant**.

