When start and/or end dates of a medication intake are missing, the medication is considered as concomitant with the study vaccination schedule.

If the first study vaccination date is missing then the medication is considered as concomitant with the study vaccination schedule, provided that the study vaccine was administered to the subject.

For further details please refer to the technical and program specifications document stored in ^{PPD} within the SAS Drug Development (SDD) server.

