13.3 Unsolicited Adverse Events

The analysis will use unsolicited adverse event data from all reporting sources combined.

All the unsolicited AEs occurring during the study, judged either as probably related, possibly related, or not related to vaccination by the investigator, will be recorded. The original verbatim terms used by investigators to identify AEs in the CRFs will be mapped to preferred terms using the MedDRA dictionary. The unsolicited AEs will then be grouped by MedDRA preferred terms into frequency tables according to SOC.

All AEs will be summarized by vaccine group, according to SOC and PT within SOC. When an unsolicited AE occurs more than once for a subject, the maximal severity and strongest relationship to the vaccine group will be counted.

Only vaccine-emergent AEs will be analyzed, i.e., excluding those after a subject has given informed consent but before vaccination. The selection of unsolicited adverse events and the assignment to time intervals will be done by day of onset and not by days ongoing/persisting.

The summaries will be presented by period of onset and will include frequency distributions of the different adverse events:

- Vaccination 1 AEs, Onset between day 1 and day 28.
- Vaccination 2 AEs, Onset between day 29 and day 57.
- After either vaccination, Onset between day 1 and day 57
- Onset after day 57 through study end.
- At any time during the study, Onset after vaccination 1 on day 1

The analysis of unsolicited adverse events comprises the following categories:

- Any unsolicited adverse event.
- Possibly or probably related unsolicited adverse events.
- Unsolicited adverse events leading to death.

- Serious adverse events.
- Possibly or probably related serious adverse event.
- Unsolicited adverse events leading to premature withdrawal from study.
- Unsolicited adverse events leading to dose reduction, interruption or delay in study vaccination.
- Unsolicited adverse events leading to hospitalization.
- Unsolicited adverse events leading to new onset of chronic disease.
- Unsolicited adverse events of special interest.
- Medically attended adverse events.

Solicited adverse events continuing beyond day 7 will be coded by MedDRA and combined with the respective unsolicited adverse events.

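### SAP section 8.7 lets a missing or same-month partial start date override, or conflict with, an end date known to fall before the first vaccination, for adverse events and for medications

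*SAP*

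**What the plan says.** All of the derivation rules are in SAP section 8.7, and the wording at issue is the same in all three SAP versions in the file.

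- **Adverse events, start missing:** "If an adverse event start date is missing or unknown, the adverse event will be considered as emergent". The end date is not mentioned.
- **Adverse events, dates partly known:** "When start and/or end dates of an adverse event are only partially known, adverse events will be categorized as emergent before, during, or after vaccination", by two rules. If a partial end date lies in a year or month before that of the first vaccination, "then the adverse event is emergent before vaccination phase". If a partial start date lies in the same year or month as the first vaccination, or later, the event is emergent during the vaccination phase.
- **Medications, definition:** a previous medication "is a medication used only before the first study vaccination (i.e. medication end date < first study vaccination date"). Everything else is concomitant.
- **Medications, dates missing:** "When start and/or end dates of a medication intake are missing, the medication is considered as concomitant with the study vaccination schedule".

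Section 13.3 states the purpose of the adverse event classification: "Only vaccine-emergent AEs will be analyzed, i.e., excluding those after a subject has given informed consent but before vaccination". Section 13.6 tabulates concomitant medications by vaccine group.

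**The concern.** If a record's end date is before the first vaccination, the event or drug use was over before dose 1, whatever its start date. Section 8.7 does not use that information consistently. For some records the rules place an event in the emergent class although the recorded dates show it had ended. For others, two rules give opposite answers and the programmer must choose.

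Such records can arise. Prior medications are recorded at screening (Day -28 to -3), and medically attended events are collected from the signing of consent (Table 3-1, footnote o). At stake are the counts of vaccine-emergent events and of concomitant medications, which could include items that cannot have followed vaccination. Two programmers working from the same text could also produce different tables.

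**Working it through.** The plan states no figure on this point, so the check is to apply the section 8.7 rules to each combination of dates. For illustration, take dose 1 on 20 April.

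| Record | Start | End | Result under section 8.7 |
|---|---|---|---|
| AE 1 | missing | 10 April | Emergent by the missing-start rule. No other rule applies, because neither date is partial. |
| AE 2 | missing | March, day unknown | Emergent by the missing-start rule; before vaccination by the partial-end rule. Conflict. |
| AE 3 | April, day unknown | 12 April | Emergent during the vaccination phase by the partial-start rule, because the month is the same. The partial-end rule does not apply, because the end date is complete. |
| AE 4 | missing | missing, or after dose 1 | Emergent. A reasonable default. |
| Drug 1 | missing | 15 February | Previous by the definition; concomitant by the missing-date rule. Conflict. |
| Drug 2 | missing | missing, or after dose 1 | Concomitant under both. No problem. |

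**Adverse events.** AE 1 ended 10 days before dose 1 (20 - 10) and AE 3 ended 8 days before (20 - 12), yet the stated rules class both as emergent. AE 2 has a vaguer end date than AE 1 but has at least one rule that places it correctly, so the more precise record is handled worse. In the missing-start rule the word emergent is not tied to a phase. It is read as vaccine-emergent through section 13.3.

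**Medications.** The definition looks only at the end date ("medication end date < first study vaccination date"). The missing-date rule covers a missing start, a missing end, or both, so it includes a missing start with a known end. Both sentences apply to Drug 1, and neither is said to come first.

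**Size per subject.** The input is 24 subjects per group (section 4.1). One affected subject changes a row by at most 1/24 = 0.0417, or 4.2 percentage points. This is a ceiling: the row rises only if the subject would not otherwise be counted in it. Section 8.7 counts repeated events with the same preferred term once per subject, and a subject with another concomitant drug is already in any overall row.

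**Which adverse event tables.** Section 13.3 assigns events to intervals by day of onset. AE 1 and AE 2 have no onset day, so they would most plausibly enter only the summary for any time during the study.

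**The case against.** Five points can be made for the plan.

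- **The direction is cautious.** Section 8.7 also treats missing severity as severe and missing relationship as related. Counting undatable records as emergent or concomitant fits that approach, and it cannot hide a post-vaccination event. This stands for records that cannot be dated. It does not justify the result when the end date is known to precede dose 1.
- **Details are left to another document.** Section 8.7 refers to technical and program specifications that are not at hand and may set the order of the rules. It follows that wrong output cannot be shown. The SAP's own sentences still conflict.
- **Few adverse events can be affected.** In Table 3-1 the row for assessing all adverse events starts at Day 1, and only medically attended events are collected from consent. This stands.
- **The tables are descriptive.** Section 8.4 uses tests for description only, and subjects are randomised to vaccine groups within each cohort, so these errors have no evident reason to favour one group. The primary immunogenicity analysis does not use these classes. This stands.
- **The text already gives some right answers.** A reader might infer that every adverse event or drug with a missing start and an end before dose 1 is counted as post-vaccination. The SAP does not support that. The partial-end rule places some of these events before vaccination, and the definition of previous medication depends on the end date alone. For those records the fault is an unresolved contradiction, not a settled misclassification.

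**Conclusion.** The point holds, and it is minor. There are two kinds of fault:

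- **Wrong class under the stated rules:** adverse events with a missing start, or a start known only to the vaccination month, and a complete end date before dose 1. This runs against section 13.3.
- **Contradiction without precedence:** adverse events with a missing start and a partial end date before dose 1, and medications with a missing start and a known end date before dose 1.

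The effect is limited to descriptive safety and medication tables, at most 4.2 percentage points per affected subject in one group's row, assuming the planned 24 subjects. A reader might go on to infer a typical number of misplaced subjects per group. The SAP gives no frequency for such records, so no such number can be supported. The verdict rests on the SAP text alone; the separate program specifications may already resolve the order of the rules.

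**What to change.** Add one rule to section 8.7, covering adverse events and medications alike: if the end date, complete or partial, places the end before the first vaccination, the event is pre-vaccination or the medication is previous, whatever the start date. The emergent or concomitant default then applies only when the end date is missing, is recorded as ongoing, or cannot be placed before the first vaccination. State also that an adverse event recorded as worsening after vaccination stays emergent, as section 8.7 already provides.

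This keeps the cautious default for every record that cannot be dated. It costs one or two sentences in the SAP and one condition in the derivation, plus a check that the program specifications agree. No data collection or other analysis changes.

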8.8 Analysis Software

All analyses will be performed using SAS Software version 9.1 or higher.

8.9 Data Transformation

Distributions of antibodies are generally skewed to the right (Nauta, 2010). Therefore, prior to any statistical analysis that assumes normally distributed observations, antibody titers will be log₁₀-transformed. GMTs and their 95% confidence intervals (CIs) are computed by exponentiating (base 10) the least squares means and 95% CIs of the log₁₀ titers.

9. STUDY SUBJECTS

9.1 Disposition of Subjects and Withdrawals

All subjects who provide informed consent will be accounted for in this study. The frequencies and percentages of subjects in each analysis set, study withdrawals, subgroups, and major protocol deviations will also be presented.

The time the subjects are under observation will be summarized by vaccine and overall using summary statistics (mean, SD, minimum, median, maximum).

10. DEMOGRAPHICS AND OTHER BASELINE CHARACTERISTICS

10.1 Demographics

Age, height, weight, body mass index will be summarized by reporting the mean, standard deviation, median and range, and will be calculated by vaccine group and overall for each cohort.

The frequencies and percentages of subjects by sex, ethnic origin, race, entry criteria fulfilled will be presented by vaccine group and overall for each cohort. Demographic data will be tabulated for the All Enrolled, FAS, PPS, EXP and Safety sets.

10.2 Medical History

The frequencies and percentages of subjects with medical history will be presented by MedDRA system organ class (SOC) and preferred term (PT), by vaccine group and overall for each cohort. Medical history data will be tabulated for the All Enrolled Set.

11. IMMUNOGENICITY ANALYSIS

11.1 Blood Samples

The frequencies and percentages of subjects with blood draws will be summarized overall and by vaccine group for each cohort. Data will be tabulated for the All Enrolled set.

11.2 Primary Objectives Analysis

Primary Objective:

To evaluate the serum neutralizing antibody (NAb) response to the RSV F subunit vaccine or placebo at Day 57 (28 days after the second dose).

Primary Immunogenicity Endpoints:

- Geometric mean titer (GMT) of the serum anti-RSV neutralizing antibody (NAb) titer at Day 57 (28 days after the second dose).
- Proportion of subjects with a ≥ 4 -fold increase in serum anti-RSV NAb titer from Day 1 (baseline) to Day 57 (28 days after the second dose).

It is assumed that log-transformed antibody titers are normally distributed; therefore values will be logarithmically transformed (base10) and all statistical analyses on antibody levels will be performed on the logarithmic scale.

Statistical models:

GMTs:

For each treatment group, GMTs of the serum anti-RSV NAb along with their associated 95% CIs will be computed by exponentiation of the corresponding log-transformed means and 95% CIs. In addition, median, minimum and maximum values will be calculated for each vaccine group at each time-point.

Adjusted GMTs for adjuvant groups within each cohort (dosage level) separately will come from an ANCOVA model including fixed factor for adjuvant and covariate adjustment for baseline value.

The following SAS® code will be used for the ANCOVA model:

```
PROC GLM data = dataset;  
BY cohort antigen visitnum;  
class adjuvant;  
model logtiter_post = adjuvant logtiter_pre;  
LSMEANS adjuvant / stderr cl OUT=LSMEANS;
```

RUN;

Adjusted GMTs for dosage groups within each adjuvant separately will come from an ANCOVA model including fixed factor for dosage and covariate adjustment for baseline value.

The following SAS® code will be used for the ANCOVA model:

```
PROC GLM data = dataset;  
BY adjuvant antigen visitnum;  
class dosage;  
model logtiter_post = dosage logtiter_pre;  
LSMEANS dosage / stderr cl OUT=LSMEANS;  
RUN;
```

The factorial design of the study allows fitting a statistical model able to evaluate the impact of each factor in explaining the antibody response; the following analysis of covariance (ANCOVA) model will be utilized:

$$Y_{ijk} = \mu + \alpha_i + \beta_j + \gamma X_{ijk} + t_{ijk}$$

where Y_{ijk} represents the log-transformed (base 10) titer of the k^{th} subject in the dosage group i ($i= 45\mu\text{g}, 90\mu\text{g}$ or $135\mu\text{g}$) and adjuvant group j ($j=$ no adjuvant, aluminum or MF59); μ is the overall mean; α_i is the main effect of dosage i ; β_j is the main effect of adjuvant j , γ is a parameter included to adjust for continuous covariate X_{ijk} representing baseline titer; t_{ijk} are error terms normally distributed with mean zero and variance σ^2 .

The following SAS® code will be used for the ANCOVA model:

```
PROC GLM data = dataset;  
BY antigen visitnum;  
class dosage adjuvant;  
model logtiter_post = dosage adjuvant logtiter_pre;  
LSMEANS dosage adjuvant / stderr tdiff cl pdiff OUT=LSMEANS;  
ESTIMATE "dose 45 vs dose 90" dose 1 -1 0;  
ESTIMATE "dose 90 vs dose 135" dose 0 1 -1;  
ESTIMATE "dose 45 vs dose 135" dose 1 0 -1;  
ESTIMATE "no adj vs alum" adjuvant 1 -1 0;  
ESTIMATE "alum vs MF59" adjuvant 0 1 -1;  
ESTIMATE "no adj vs MF59" adjuvant 1 0 -1;  
RUN;
```

where `logtiter_post` represents the log-transformed antibody value of the immunogenicity variable at a given post baseline timepoint, `dosage` indicates the amount of vaccine content, `adjuvant` the type of adjuvant (i.e none, aluminum hydroxide or

MF59), `logtiter_pre` the log-transformed antibody baseline value of the immunogenicity variable.

Placebo will not be considered in this analysis.

Analysis of interaction:

To test for a possible effect modifier, a dosage by adjuvant interaction will be added to the previous ANCOVA model. With an overall p-value smaller than 0.05, further investigations will be conducted to better understand the degree of the interaction. Additional examinations will include point estimates and 95% CIs for the different levels (e.g. low dosage by no adjuvant, low dosage by alum and so forth) of the factors under study.

4-fold increase:

Proportions of subjects with a ≥ 4 -fold increase in serum anti-RSV NAb titer from baseline will be presented, for each treatment group within each cohort, together with their two-sided 95% Clopper-Pearson CIs (Clopper, 1934). Group differences will not be produced.

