The purpose of this study is to evaluate the safety and immunogenicity of two doses of the investigational RSV F subunit vaccine administered intramuscularly (IM). In this current Phase 1, first-in-human study, the three different antigen amounts that have been selected will be evaluated in a stepwise manner in three different cohorts (cohort 1: low dosage of RSV F subunit vaccine [45 µg], cohort 2: middle dosage of RSV F subunit vaccine [90 µg], and cohort 3: high dosage of RSV F subunit vaccine [135 µg]). In addition, the effect of an adjuvant, either aluminum hydroxide or MF59, and antibody kinetics post-vaccination at different time points will be evaluated as compared to unadjuvanted RSV F subunit vaccine at the same dosage levels.

For further details please refer to [section 1.0 of the protocol](#).

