3. STUDY DESIGN

This is a Phase 1, randomized, observer blind, placebo-controlled, dosage-escalation, single center study, enrolling healthy adults. In total, approximately 288 healthy non-pregnant female and male adults (18 to 45 years of age) will be enrolled in the study in the ratio of 3:1. There is a higher ratio of female to male subjects because the RSV F subunit vaccine is ultimately intended for use in pregnant women. Men are still being included in this study because the vaccine may also be tested in the future in elderly subjects.

Approximately 288 healthy subjects will be enrolled (1:1:1) in a stepwise dosage-escalation manner in to one of three cohorts (cohort 1: low dosage of RSV F subunit vaccine [45 µg], cohort 2: middle dosage of RSV F subunit vaccine [90 µg], and cohort 3: high dosage of RSV F subunit vaccine [135 µg]). Cohort 1 will be enrolled first, followed by cohort 2, and finally cohort 3. Within each cohort subjects will be randomly allocated (1:1:1:1) to receive vaccine with no adjuvant, vaccine with aluminum hydroxide, vaccine with MF59, or saline placebo, as outlined in [Table 4-1](#). All subjects will receive two doses of a 0.5 mL intramuscular injection of the vaccine, with adjuvant (aluminum hydroxide [1 mg] or MF59 [0.25 mL; 9.75 mg squalene and surfactants]), the vaccine without adjuvant, or saline placebo. There will be approximately 24 subjects in each active treatment group and 24 placebo subjects per cohort) ([Table 4-1](#)).

The schedule of time and events, including whether a visit is a telephone call or a clinic visit is displayed in [Table 3-1](#).

Table 3-1: Times and Events Table

Study Period	Screen	Vaccine Dose #1 & Safety Follow-up				Vaccine Dose #2 & Safety Follow-up					Post-vaccination Follow-up				
		Clinic Visit	Clinic Visit	Reminder Call	Clinic Visit	Phone Call	Clinic Visit	Reminder Call	Clinic Visit	Phone Call	Clinic Visit	Clinic Visit	Clinic Visit	Clinic Visit	Clinic Visit
Study Day	-28 to -3	1	3, 5	8	15, 22	29	31, 33	36	43, 50	57	85	113	181	209	271, 366, 394
Days post 1 st dose		0	2, 4	7	14, 21	28	30, 32	35	42, 49	56					
Days post 2 nd dose						0	2, 4	7	14, 21	28	56				
Study Visit Window (min-max) in Days (d)	n/a	n/a	-1/+1	-1/+4 d	-1/+1	+14 d	-1/+1	-3/+3 d	-1/+1	-7/+7 d	-7/+7 d	-7/+7 d	-7/+7 d	-14/+14 d	-7/+7 d
Visit Number	Screening	1		2	3, 4	5		6	7, 8	9	10	11	12	13	14, 15, 16
Informed Consent	X														
Medical History	X														
Physical Exam ^a	X	X ^b		X		X ^b		X		X	X	X	X	X	

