4. RANDOMIZATION AND BLINDING

4.1 Method of Group Assignment and Randomization

Subjects will be enrolled in a stepwise dosage-escalation manner into one of three cohorts:

- Cohort 1: low dosage of RSV F subunit vaccine [45 µg],
- Cohort 2: middle dosage of RSV F subunit vaccine [90 µg], and
- Cohort 3: high dosage of RSV F subunit vaccine [135 µg]).

Within each cohort, subjects will be randomly allocated (1:1:1:1) to receive vaccine with no adjuvant, vaccine with aluminum hydroxide, vaccine with MF59, or placebo, as outlined in [Table 4.1](#). All subjects will receive two doses of a 0.5 mL intramuscular injection of the vaccine with adjuvant (aluminum hydroxide [1 mg] or MF59 [0.25 mL; 9.75 mg squalene and surfactants]), the vaccine without adjuvant, or saline placebo. There will be approximately 24 subjects in each active treatment group, and 24 placebo subjects in each cohort.

Table 4.1.

Cohort	Dosage	Route of Administration	Regimen: Two Doses †		
			No Adjuvant	Al(OH) ₃ ‡	MF59 ‡
1	45 µg	IM (0.5 mL)	24	24	24
	Placebo (saline)	IM (0.5 mL)	24		
2	90 µg	IM (0.5 mL)	24	24	24
	Placebo (saline)	IM (0.5 mL)	24		
3	135 µg	IM (0.5 mL)	24	24	24
	Placebo (saline)	IM (0.5 mL)	24		

For further details please refer to [section 5.1. of the protocol](#).

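### The second primary endpoint (≥4-fold NAb rise at Day 57) has no planned estimate or interval for the randomised within-cohort comparisons

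*SAP*

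**What the plan says.** Section 11.2 names two primary immunogenicity endpoints: the Day 57 GMT of neutralizing antibody (NAb), and the proportion of subjects whose titer rises at least 4-fold from baseline to Day 57. The proportion is reported per treatment group within cohort, each with its own two-sided 95% Clopper-Pearson interval. The paragraph ends "Group differences will not be produced". This stands in the latest SAP text in the file, and no other section supplies a contrast for this endpoint. Section 11.3 presents the secondary proportions per group in the same way.

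Two other places bear on it:

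- Section 1 says that the effect of an adjuvant "will be evaluated as compared to unadjuvanted RSV F subunit vaccine at the same dosage levels".
- Section 4.1 says: "Within each cohort, subjects will be randomly allocated (1:1:1:1) to receive vaccine with no adjuvant, vaccine with aluminum hydroxide, vaccine with MF59, or placebo". On group size it says: "There will be approximately 24 subjects in each active treatment group, and 24 placebo subjects in each cohort".

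Section 8.4 makes statistical tests descriptive only and drops multiplicity adjustment.

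**The concern.** The design supports two kinds of randomised, concurrent comparison inside each cohort: adjuvanted against unadjuvanted vaccine at one dosage, and vaccine against placebo. The first is a stated purpose of the study. For the responder endpoint the plan provides neither an estimate nor an interval for either one. Elsewhere it does plan differences: the factorial ANCOVA has adjuvant and dosage contrasts for GMT, and section 11.4 has Hodges-Lehmann pairwise differences with 95% intervals for the B-cell endpoints.

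Readers of the report will want to compare arms on a primary endpoint. If the tables hold only separate intervals, the natural shortcut is to see whether they overlap. That is much stricter than a 95% comparison, so a moderate adjuvant effect could be read as no difference. Anyone who instead computes a difference from the counts will choose the interval method after seeing the data.

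**Working it through.** **Inputs.** From section 4.1: n = 24 per arm, 4 arms per cohort, 3 cohorts. From section 11.2: two-sided 95% Clopper-Pearson intervals. The SAP gives no response rates, so all rates below are assumptions shown over a range.

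**The plan's own figure.** 3 cohorts × 4 arms × 24 = 288, which agrees with the total in section 3. The SAP states no power or detectable difference for this endpoint, so there is nothing further to reproduce.

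**Formulas.**

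- Clopper-Pearson for x of n: lower limit = 2.5% quantile of Beta(x, n − x + 1); upper limit = 97.5% quantile of Beta(x + 1, n − x).
- Newcombe for d = p1 − p2, with Wilson limits (l, u) for each arm: lower = d − √[(p1 − l1)² + (u2 − p2)²]; upper = d + √[(u1 − p1)² + (p2 − l2)²].

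**Example 1: 18/24 v 10/24.** The Clopper-Pearson intervals are 53–90% and 22–63%, which overlap. The Wilson limits are 0.551–0.880 and 0.245–0.612, and d = 0.750 − 0.417 = 0.333.

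- Lower: 0.333 − √(0.199² + 0.195²) = 0.333 − 0.279 = 0.05.
- Upper: 0.333 + √(0.130² + 0.172²) = 0.333 + 0.216 = 0.55.

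The difference is 33 points (5 to 55), which excludes zero.

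**Example 2: 6/24 vaccine v 0/24 placebo.** The Clopper-Pearson intervals are 10–47% and 0–14%, which overlap. The Newcombe difference is 25 points (6 to 45), which excludes zero.

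**Exact enumeration.** Over all 25 × 25 outcomes of two independent Binomial(24, p) arms, sum the probability that (a) the two Clopper-Pearson intervals do not overlap, (b) the Newcombe interval excludes zero, and (c) Fisher's exact test gives p ≤ 0.05.

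| True rates | (a) Non-overlap | (b) Newcombe | (c) Fisher |
|---|---|---|---|
| 50% v 50% | 0.2% | 6.0% | 2.9% |
| 70% v 50% | 5% | 31% | 21% |
| 70% v 40% | 16% | 59% | 47% |
| 75% v 40% | 27% | 73% | 62% |
| 80% v 40% | 42% | 84% | 76% |
| 30% v 5% | 19% | 67% | 56% |
| 40% v 5% | 48% | 89% | 82% |
| 50% v 5% | 76% | 98% | 95% |
| 60% v 5% | 93% | 99.7% | 99% |

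With equal true rates, non-overlap occurs about 0.2% of the time, so as a comparison rule it is far stricter than its 95% label suggests. The loss is large for differences of about 20 to 35 points and small when a low placebo rate is set against a rate of 60% or more.

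**What the GMT endpoint offers instead.** The within-cohort ANCOVA in section 11.2 requests adjusted means with intervals and no pairwise differences. Differences come only from the main-effects factorial model, which averages adjuvant effects over the three dosages and leaves placebo out. GMT therefore has no explicit same-dosage or placebo contrast that could stand in for the missing one.

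**The case against.** The strongest reply is that the plan is openly descriptive. The primary immunogenicity objective is to evaluate the response, with no hypothesis, and section 8.4 limits the role of tests. A proportion per arm with an exact interval meets that objective in Phase 1. The adjuvant sentence in section 1 names no endpoint, and contrasting the continuous titer while only describing its dichotomised form is defensible. All of that stands, and it is why this is not an error or a contradiction. It does not make the omission a good choice: a difference with an interval is itself descriptive, and section 8.4 did not keep the plan from producing differences for other endpoints.

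Three stronger readings are tempting, and the document supports none of them.

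- A reader might infer that the arms can be compared only by eye. The sentence limits which outputs are produced. Counts per arm let anyone compute a difference, and the SAP never tells readers to judge by overlap.
- A reader might infer that separate intervals miss most real differences. That depends on effect size and fails for large placebo contrasts (93% shown at 60% v 5%).
- A reader might infer that the two primary endpoints could disagree merely because GMT has difference intervals and the proportion has none. For the same-dosage and placebo contrasts, GMT has none explicitly planned either.

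The size of the gap also depends on the comparator. Newcombe is slightly anticonservative here (6.0% at 50% v 50%). Against Fisher's test the gap is smaller but remains: 62% against 27% at 75% v 40%.

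**Conclusion.** The point holds as a weak descriptive choice. A primary endpoint has no planned estimate or interval for comparisons that the design randomises, one of which section 1 gives as a purpose. Under assumed rates and 24 per arm, relying on separate intervals lowers the chance of showing a difference from 59% to 16% at 70% v 40%, and from 73% to 27% at 75% v 40%. For large vaccine-placebo differences the practical loss is small.

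Part of the weakness is sample size and would remain: even the Newcombe interval shows 70% v 50% only 31% of the time. The figures also take all 24 subjects per arm as evaluable, whereas section 8.2.2 makes the per-protocol set the principal set, so actual numbers may be lower. The change is a cheap improvement and not a correction that the analysis depends on.

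**What to change.** In section 11.2, replace the sentence that rules out group differences with wording such as:

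*Within each cohort, differences in the Day 57 ≥4-fold response proportion will be presented with two-sided 95% confidence intervals for alum v no adjuvant, MF59 v no adjuvant, and each vaccine group v the concurrent placebo group. These are descriptive; no p-values and no multiplicity adjustment.*

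Name one interval method in advance, either Miettinen-Nurminen or Newcombe. Because section 11.3 refers back to the primary methods, also state whether the differences extend to the secondary proportions or stay with Day 57 NAb.

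The cost is a sentence in the SAP and extra columns in existing tables, with no new data. The downside is (2 + 3) × 3 = 15 additional unadjusted intervals for the primary endpoint. Section 8.4 already accepts unadjusted descriptive results, but the tables should label these intervals as such. The small groups will still leave them wide.
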